8.4.5. Product Complaints

A product complaint is any written, electronic, or oral communication that alleges deficiencies related to the identity, quality, durability, reliability, safety, effectiveness or performance of a trial intervention. The sponsor collects product complaints on investigational products and drug delivery systems used in clinical studies in order to ensure the safety of study participants, monitor quality, and to facilitate process and product improvements. Participants will be instructed to contact the investigator as soon as possible if he or she has a complaint or problem with the investigational product or drug delivery system so that the situation can be assessed.

Time Period for Detecting Product Complaints

- Product complaints that result in an adverse event will be detected, documented, and reported to the sponsor during all periods of the study in which the drug is used.
- If the investigator learns of any product complaint at any time after a participant has been discharged from the study, and such incident is considered reasonably related to a drug provided for the study, the investigator will promptly notify the sponsor.

Prompt Reporting of Product Complaints to Sponsor

- Product complaints will be reported to the sponsor within 24 hours after the investigator becomes aware of the complaint.
- The Product Complaint Form will be sent to the sponsor.

Follow-up of Product Complaints

- Follow-up applies to all participants, including those who discontinue study intervention.
- The investigator is responsible for ensuring that follow-up includes any supplemental investigations as indicated to elucidate the nature and/or causality of the product complaint.
- New or updated information will be recorded on the originally completed form with all changes signed and dated by the investigator and submitted to the sponsor

8.4.6. Pregnancy

The Investigator must notify the Sponsor immediately regarding a pregnancy in a (1) female clinical trial patient or (2) female partner of a male clinical trial patient.

Pregnant female patients must be withdrawn from study drug.

If a female partner of a male patient becomes pregnant or suspects she is pregnant by the male patient, the male patient will be advised by the study Investigator to have his female pregnant partner inform her treating physician immediately.

The Investigator must perform medical assessments as clinically indicated and continue to follow the patient for ≥ 4 weeks after delivery. Medical details for both the mother and baby must be obtained.

The Investigator must complete a study-specific Pregnancy Form upon confirmation of a pregnancy. Pregnancy reporting forms will be provided to the site.

8.4.7. Hypersensitivity Reactions

Patients experiencing any hypersensitivity reaction should receive appropriate symptomatic medical care, as needed. Patients should be instructed to inform the site if a hypersensitivity reaction occurs. At the next study visit, a blood sample must be collected for immunogenicity analysis. The Sponsor or designee should be immediately consulted, particularly if the

hypersensitivity reaction might be attributed to the study drug, and particularly if the reaction is severe, for discussions about discontinuing the study medication.

8.5. PK and ADA Sampling

Serum PK and ADA samples will be collected in all patients. Positive ADA results may be further evaluated for neutralizing antibodies. The procedural instructions will be provided in a separate PK and Serum Antibody Sampling manual.

8.6. Study Termination

The Sponsor has the right to terminate the study at any time. Should the study be terminated, the decision and reason will be communicated in writing by the Sponsor to the Investigator and request that all patients be discontinued. Patients should be scheduled for an Early Termination visit. The entire study will be stopped if:

- Evidence has emerged that, in the collective opinion of the Investigators at each site with the concurrence of the Sponsor, or the sole opinion of the Sponsor, continuation of the study is unnecessary or unethical
- The stated objectives of the study are achieved
- The Sponsor discontinues the development of the study drug

All data available for the patient at the time of study discontinuation must be recorded in the patient's records and the eCRF.

8.6.1. Early Termination of Study Patients

The Investigator will make reasonable efforts to keep each patient in the study. However, patients may terminate or be terminated early from the study for the following reasons:

- Voluntarily withdrawal of consent to participate in the study participation, at any time
- Adverse event, laboratory abnormality or inter-current illness which, in the opinion of the Investigator, indicates that continued treatment and/or participation in the study is not in the best interest of the patient
- Serious protocol violation, persistent non-compliance or requirement for medication or procedure prohibited by the protocol
- Lost to follow-up

Patients who are terminated early from the study will have an Early Termination visit scheduled as soon as possible (see Section 7.12). All information, including the reason for early termination will be recorded in the patient's study records and in the eCRF.

Two attempts of contact (e.g., telephone contact) followed by a certified letter of contact to the patient must be documented in a patient's study records for all patients who are believed to be lost to follow-up.

8.6.2. Study Drug Discontinuation

Study drug must be discontinued for patients who experience the following:

- Inter-current illness that would, in the judgment of the Investigator, affect assessments of clinical status to a significant degree
- Treatment-related AEs that are clinically significant, deemed persistent, in the judgment of the Investigator
- Unacceptable toxicity
- Pregnancy
- Use of systemic rescue medication as outlined in Section 6.4

Patients who discontinue study drug permanently during study participation must be scheduled for an Early Termination visit except those receiving systemic rescue medication, as per the Section 6.4 .

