- For subjects not continuing into LTE, when subject had either week 16 or ET visit, and safety follow up visit (12 weeks after last IP administration)

The end of the study is defined as the date of the last visit of the last patient in the study shown in the Schedule of Visits and Procedures.

Figure 1: Study Schema

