6.4. Rescue Treatment for Atopic Dermatitis

The goal of this Phase 3 study is to demonstrate the efficacy and safety of lebrikizumab when used in combination with TCS for AD. However, add on rescue therapies may be needed, if the patient experiences clinical worsening of symptoms that are intolerable.

If medically necessary (i.e., to control intolerable AD symptoms), high potency TCS or systemic treatments (e.g., oral corticosteroids, phototherapy, cyclosporin, etc.) may be used. Study drug must be discontinued for patients receiving systemic rescue treatment. Patients should continue to attend all study visits and be assessed for safety and efficacy according to the schedule of events, even if rescue medication is initiated.

Patients using topical or systemic rescue medication who complete the study through Week 16 will be eligible to continue to a separate long-term extension study after the Week 16 visit has been completed.

All rescue treatment usage must be captured in the eCRF.

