7.11. Week 26 (\pm 3 Days) / Safety Follow-up

This visit is only applicable to patients who terminate early from the study or do not enroll in the long-term extension study, DRM06-AD07. Patients will undergo a safety follow-up visit approximately 12 weeks after the last study drug injection.

- Review and record AEs and concomitant medications and procedures that were ongoing at study termination
- Draw blood samples for PK and ADA testing.

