### 6.1.2. General Considerations for Analyses

Treatment period starts after the first injection of study treatment at Baseline Visit (Day 1) and ends after patient completed Week 16 visit or the early termination visit (ETV) (between Day 1 and Week 16). For patients who are randomized but not dosed, the Double-Blinded Treatment Period starts on the date of randomization.

Baseline will be defined as the last available value before the first injection for efficacy and health outcome analyses. In most cases, this will be the measure recorded at Baseline Visit (Day 1). If the patient does not take any injection, the last available value on or prior to randomization date will be used. Change from baseline will be calculated as the visit value of interest minus the baseline value.

For Pruritus Numeric Rating Scale (NRS) and Sleep-Loss due to Pruritus collected via eDiary, the baseline period is the 7-day window prior to the first injection. A patient must have responses on at least 4 of 7 days to calculate a baseline weekly mean. If a patient has responses for 3 or fewer days, the baseline mean value will be considered missing. eDiary data for Pruritus NRS and Sleep-loss due to Pruritus are mapped to study visit per [Appendix 1](#).

For the safety analyses, the following baselines will be used. For safety analyses using a baseline period, the baseline period is defined as the time from Screening Visit to the date/time of the first injection in Treatment Period.

- Treatment-emergent adverse events (TEAEs): baseline will be all results recorded during the baseline period.
- Treatment-emergent abnormal laboratory and vital signs results: baseline will be all results recorded during the baseline period.
- Change from baseline to last observation or to each scheduled post baseline visit for laboratory and vital signs results: baseline will be the last scheduled non-missing assessment recorded during the baseline period.

The randomization to treatment groups is stratified by geographical region (US versus EU versus rest of world), age group (adolescent patients 12 to <18 years versus adults  $\geq 18$  years) and baseline disease severity (IGA 3 versus 4) as described in Section 5.3. The countries will be categorized into geographic regions for analysis (Section 6.3). Unless otherwise specified, the statistical analysis models for Treatment Period will adjust for geographic region, age group and baseline disease severity.

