### 6.2.1. Primary Estimand (Hybrid)

The primary estimand is a hybrid estimand representing the primary clinical question of interest: What is the difference between treatment conditions (that is, lebrikizumab vs placebo) in the target patient population in successful responses or means after 16 weeks achieved without use of rescue medication, and if all patients continued with treatment except those who discontinued due to lack of efficacy?

The primary estimand is described by the following attributes:

- Population: Defined through appropriate inclusion/exclusion criteria to reflect the targeted patient population for approval
- Endpoint: Apply to all primary and major secondary endpoints
- How to account for ICEs
  - Subjects who require any use of rescue medication or discontinued treatment due to lack of efficacy prior to Week 16 will be considered as treatment failures, that is, nonresponder, after the ICEs. Therefore, composite strategy is used for these types of ICEs.
  - For subjects who discontinue treatment due to reasons other than lack of efficacy prior to Week 16, a hypothetical strategy will be used to estimate what the treatment effect would have been if subjects continued with treatment. Therefore, hypothetical strategy is used for these types of ICEs.
- Population-level summary: Difference in response proportions or means between treatment conditions.

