**Table KGAD.6.3. Description of Primary and Supportive Estimands**

Estimand	Analysis Strategy for Intercurrent Events			Missing Data Imputation Method
	Rescue Medication	Treatment Discontinuation		
		Due to Lack of Efficacy	Due to Any Other Reasons	
Primary Estimand (Hybrid)	Composite: Set to baseline	Composite: Set to baseline	Hypothetical: Set to missing	Primary analysis: MCMC-MI Sensitivity analysis: Tipping point analysis
Supportive Estimand for	Composite:	Composite:	Composite:	NRI

Categorical Endpoints (Composite)	Set to nonresponder	Set to nonresponder	Set to nonresponder	
Supportive Estimand for Continuous Endpoints (Hypothetical)	Hypothetical: Set to missing	Hypothetical: Set to missing	Hypothetical: Set to missing	MMRM, LOCF

Abbreviations: LOCF = last observation carried forward; MCMC-MI = Markov chain Monte Carlo multiple imputation; MMRM = mixed-model repeated measures; NRI = nonresponder imputation.

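### Protocol 8.6.2 treats stopping study drug as leaving the study, so patients who stop without systemic rescue have no Week 16 outcome by design and no treatment-policy analysis is possible for them

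*Protocol*

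**What the plan says.** Protocol 8.6.2 lists the reasons for which study drug must be stopped: intercurrent illness, persistent treatment-related adverse events, toxicity, pregnancy and systemic rescue. It then adds: "Patients who discontinue study drug permanently during study participation must be scheduled for an Early Termination visit except those receiving systemic rescue medication".

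For rescue patients Protocol 6.4 says the opposite: "Patients should continue to attend all study visits and be assessed for safety and efficacy according to the schedule of events". This includes those whose study drug is stopped because the rescue was systemic.

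Four places show what the Early Termination (ET) visit means in practice:

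- Protocol 7.12 describes it as the visit for patients who discontinue the study, and the eDiary is handed in there.
- SAP 6.1.2 says the treatment period "ends after patient completed Week 16 visit or the early termination visit (ETV").
- Protocol 3 counts a patient not entering the extension as a completer "when subject had either week 16 or ET visit, and safety follow up visit". The ET visit thus stands in for Week 16.
- Protocol 7.11, the later safety visit, consists of a review of adverse events and concomitant medication plus one sampling step, "Draw blood samples for PK and ADA testing". It has no IGA or EASI.

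Protocol 8.6.1 asks the investigator to make reasonable efforts to keep each patient in the study.

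In the SAP the reason for stopping decides the handling. In Section 6.2.1, patients who use rescue or who "discontinued treatment due to lack of efficacy prior to Week 16 will be considered as treatment failures"; their values are set to baseline. For other stops, "a hypothetical strategy will be used to estimate what the treatment effect would have been if subjects continued with treatment", and Table KGAD.6.3 gives the data rule as "Hypothetical: Set to missing". Sections 6.4.1 and 6.11.1 fill these values by multiple imputation within arm under missing at random (MAR).

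**The concern.** Stopping a drug and leaving a trial are different events, and 8.6.2 treats them as one. Every reason it lists other than systemic rescue leads to the ET visit, and in the SAP those reasons fall into the class that is imputed as if treatment had gone on, unless the patient had already used rescue. The visit rule creates the gap that the imputation then fills.

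Two things are lost:

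- **Efficacy.** None of the SAP's three estimands uses an outcome observed after drug was stopped, and for these patients no such outcome is planned. A treatment-policy effect (what happened at Week 16 whether or not drug was continued) cannot be estimated.
- **Safety.** Scheduled adverse event review at the remaining visits stops in patients who may have left treatment for tolerability. SAP 6.14.2 takes the treatment period as the post-baseline period for treatment-emergent events, and the ET visit ends it.

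The protocol already has the alternative in 6.4, so no new procedure would be needed.

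**Working it through.** **Step 1. Follow-up and handling by reason for stopping.** That follow-up ends at the ET visit is inferred from Protocol 3, 7.11 and 7.12 and SAP 6.1.2 read together; 8.6.2 does not say so in words.

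| Situation | Visits after drug is stopped | Week 16 value in the primary analysis |
|---|---|---|
| Systemic rescue | all scheduled visits (6.4) | set to baseline |
| Stop for lack of efficacy, no systemic rescue | ET visit, then safety visit | set to baseline |
| Stop for another reason, earlier high-potency topical rescue | ET visit, then safety visit | set to baseline |
| Stop for another reason, no rescue | ET visit, then safety visit | set to missing, imputed under MAR |

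Only the last row depends on the MAR assumption.

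**Step 2. The plan's own figure.** Inputs from Protocol 9.12: 150 and 75 patients; IGA 0/1 rates 38% and 13%; EASI-75 rates 58% and 20%; two-sided Fisher's exact test at 0.05; stated power above 95%. Enumerating both binomial distributions gives 98.4% for IGA and 99.99% for EASI-75. The stated power is reproduced.

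**Step 3. Size of the shift.** The documents give no stop rate. Assume that a share d of each arm falls in the last row, with d from 5% to 12%. Of 225 patients that is 0.05 × 225 = 11.25 to 0.12 × 225 = 27.

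- MAR as planned: difference = 38 − 13 = 25 points at every d.
- Lebrikizumab stoppers respond at the placebo rate: difference = (1 − d) × 38 + d × 13 − 13 = 25 − 25d.
- Nonresponder imputation in both arms: (1 − d) × 38 − (1 − d) × 13 = 25 − 25d, the same difference.
- Extreme corner (every lebrikizumab stopper fails, every placebo stopper responds): shift = d × 38 + d × 87 = 125d.

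| d | Shift, placebo-like (points) | IGA difference | Fisher power | Shift, extreme corner (points) |
|---|---|---|---|---|
| 5% | 1.25 | 23.75 | 97.4% | 6.25 |
| 8% | 2.0 | 23.0 | 96.7% | 10.0 |
| 12% | 3.0 | 22.0 | 95.3% | 15.0 |

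For EASI-75 the placebo-like shift is 38d: 1.9 points at 5% and 4.56 at 12%.

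**Step 4. The extreme corner at 8%.** Lebrikizumab: 138 × 0.38 = 52.4, so about 52 of 150. Placebo: 69 × 0.13 = 9.0, plus 6, so 15 of 75. Fisher's exact test gives p = 0.030, still below 0.05.

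**The case against.** The strongest case against runs as follows.

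1. **The plan is coherent as written.** The primary estimand asks what would have happened had treatment continued. Off-drug values do not answer that question, and Table KGAD.6.3 would set them to missing even if they were collected. This stands. Longer follow-up changes neither the primary analysis nor its uncertainty.
2. **The effect is already bounded.** Nonresponder imputation makes staying on treatment part of the response definition, so a discontinuer's result is known and needs no assumption about the Week 16 value. The tipping-point grid runs from 0 to 1 in both arms and contains the extreme corner. This stands for the binary endpoints, with two limits: the tipping-point analysis runs only after a significant result, and the continuous endpoints have only MMRM as the alternative, which also assumes MAR.
3. **Not all the missing data come from 8.6.2.** Consent withdrawal and loss to follow-up (Protocol 8.6.1) would leave gaps under any wording. This stands, and the documents give no split.
4. **Safety is not abandoned.** Adverse events are followed to resolution or an acceptable level (8.4.4), serious events are recorded to the end of the study (8.4.4.4), and the ET visit itself is full. This stands; what is lost is the scheduled review between the ET visit and Week 16.
5. **It is late.** SAP Version 4 postdates the primary database lock. This stands for data recovery, but it does not remove the gap in the plan.

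A reader might also infer that every patient who stops without systemic rescue is imputed as if still treated. The SAP does not support that: lack-of-efficacy stops and topical rescue users are set to baseline. Nor do the documents support reading the 10 points at 8% as the likely error. It needs every placebo stopper to respond, against an assumed placebo rate of 13%.

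**Conclusion.** The point holds as a design weakness that was cheap to avoid. It is not an error in the primary analysis. By combining stopping drug with leaving the study, 8.6.2 makes Week 16 IGA, EASI and diary outcomes missing by design for patients who stop without systemic rescue. That sits badly with 6.4 and 8.6.1. It rules out a treatment-policy analysis for these patients and ends their scheduled adverse event review early.

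The likely numerical effect is small: about 1.25-3.0 points on a planned IGA difference of 25, with power still above 95%. This rests on three assumptions: a 5-12% stop rate that the documents do not give, equal rates in the two arms, and lebrikizumab stoppers responding at the placebo rate. Since part of that share would be missing anyway, the part due to 8.6.2 is smaller. What is affected is which effect can be reported, not whether the trial has enough power.

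**What to change.** Amend Protocol 8.6.2 so that patients who stop study drug but do not withdraw consent are asked to keep the remaining scheduled assessment visits (IGA, EASI, eDiary, adverse event review) through Week 16, as 6.4 already provides after rescue. Reserve the ET visit for patients who leave the study, which is how 7.12 describes it, and bring the treatment-period definition in SAP 6.1.2 and the completion rule in Protocol 3 into line. The rules on when study drug is stopped do not change.

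In the SAP, keep the primary estimand and add one supplementary treatment-policy analysis of IGA 0/1 and EASI-75 at Week 16, using observed values whether or not drug was continued.

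The cost is wording plus use of existing visits: at most about 11-27 patients under the assumed rates, fewer once withdrawals and losses are taken out. Some patients will decline, and IGA or EASI may be hard to interpret in those who stopped for an illness that affects assessment.

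For patients already past Week 16 the change recovers nothing. There the report should state that no treatment-policy result is available for them, and use the discontinuation tables by reason that SAP 6.7 already plans to show how many patients this concerns.

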8.7. Data Safety Monitoring Board

An independent data safety monitoring board (DSMB) comprised of members who are independent of the study sponsor and study investigators will monitor patient safety by conducting formal reviews of accumulated safety data that is blinded by treatment group; if requested, the DSMB may have access to the treatment allocation code or any other requested data for the purposes of a risk-benefit assessment.

The DSMB will provide the sponsor with appropriate recommendations on the conduct of the clinical study to ensure the protection and safety of the patients enrolled in the study. The DSMB will also institute any measures that may be required for ensuring the integrity of the study results during the study execution.

All activities and responsibilities of the DSMB are described in the DRM06 DMC charter.

9. STATISTICAL CONSIDERATIONS

9.1. General Statistical Methodology

All statistical processing will be performed using SAS[®] unless otherwise stated. Except where noted, all statistical tests will be two-sided and will be performed at the 0.05 level of significance.

Descriptive statistics will be used to provide an overview of the efficacy and safety results. For categorical parameters, the number and percentage of patients in each category will be presented. For continuous parameters, descriptive statistics will include number of subjects (n), mean, standard deviation (SD), median, minimum and maximum. Appropriate inferential statistics will be used for the primary and secondary efficacy variables. For dichotomous variables, the CMH analysis will be used. For continuous variables, an analysis of covariance (ANCOVA) will be used with factors of treatment and randomization strata and relevant baseline value. More details will be specified in the statistical analysis plan (SAP).

The Pruritus-NRS weekly mean will be calculated as follows: The mean of each patient's baseline and post-baseline Pruritus-NRS scores will be computed for each week based on the

previous 7 days. The weekly mean will be calculated if a patient has responses for Pruritus-NRS on at least 4 of the 7 days of the week. If the patient has 3 or fewer Pruritus-NRS responses, the mean value for that item will be considered missing. All Pruritus-NRS efficacy endpoint analyses will be conducted on the weekly mean. The Sleep-Loss weekly mean will be calculated similar to the Pruritus-NRS weekly mean. All Sleep-Loss efficacy endpoint analyses will be conducted on the weekly mean.

The primary method of handling missing efficacy data will be as follows for both binary and continuous endpoints: for patients who receive rescue medication (Section 6.4 for definition of rescue medication), use systemic corticosteroids or withdraw from the study due to lack of efficacy, set to the patient's baseline value subsequent to this time through Week 16. Markov chain Monte Carlo (MCMC) multiple imputation will be used to handle the remaining missing data. MCMC multiple imputation for all missing values, Last Observation Carried Forward (LOCF) and Tipping Point analysis will be used for sensitivity analyses.

Demographic data will be summarized by treatment group using descriptive statistics. Patients' baseline characteristics related to efficacy analyses will be compared with descriptive statistics among treatment groups to ensure comparable results.

The number of patients in each analysis set will be summarized. Reasons for study withdrawal during the blinded study will be summarized using frequencies and percentages by treatment group.

An SAP, describing all statistical analyses will be provided as a separate document. The SAP will be finalized prior to unblinding of the study treatments.

